4.2.1. Subgroups

Besides presenting results for all mBC patients treated with palbociclib in combination with AI patients as first-line treatment results for different subgroups split by age and comorbidities as well as disease-specific characteristics will also be presented.

These subgroups of HR+/ HER2 negative mBC patients are:

- *Patients below 65 years of age*
- *Patients 65-74 years of age*
- *Patients 75+ years of age*
- *Patients split by comorbidity severity score (CCI; 0, 1, 2, and 3 or higher (3+))*
- *Patients split by number of comorbidities (0, 1, 2+)*
- *Patients split in types of comorbidities (Cardiac disease, Vascular disease, Metabolic disease, Psychiatric disease, Blood and lymphatic system)*
- *Patients with or without visceral disease*
- *Bone only patients*
- *Endocrine resistant, endocrine sensitive or de novo patients*

4.3. Variables

The main variables included in the study are the following:

Variable	Role	Data source(s)	DBCG variable(s)
Diagnosis (ICD-10 code: DC50)	Exposure/ Inclusion	DBCG registry	Not applicable
Treatment with palbociclib	Exposure/ Inclusion	DBCG registry	RE201, RE201A
Date of birth	Baseline	DBCG registry	Based on M1
Date of breast cancer diagnosis	Baseline	DBCG registry	Not applicable
Occurrence of metastases	Baseline	DBCG registry	RE220-RE227
Visceral status (visceral and non-visceral – visceral defined as metastases in the organs, e.g., lung, liver))	Baseline	DBCG registry	RE220-RE227
Bone only	Baseline	DBCG registry	RE14
Metastatic sites (liver, lung, CNS, lymph nodes)	Baseline	DBCG registry	RE10-18 + 80-81, 117-119, 219-222
Endocrine resistant (recurrent pts with advanced disease within 12 months of completing adjuvant endocrine therapy or during adjuvant endocrine therapy)	Baseline	DBCG registry	Calculated
Endocrine sensitive (recurrent pts with advanced disease after 12 months of completing adjuvant endocrine therapy, recurrent pts who received no adjuvant endocrine therapy)	Baseline	DBCG registry	Calculated
De Novo (primary mBC – newly metastatic)	Baseline	DBCG registry	Calculated
Date of relapse	Baseline	DBCG registry	RE1-RE3
Date for treatment initiation with palbociclib	Baseline	DBCG registry	RE203-RE205
Date for treatment stop with palbociclib	Baseline	DBCG registry	RE206-RE208
Charlson Comorbidity Index (CCI) – point scores of 0, 1, 2 and 3 or higher (3+) (calculated at start of palbociclib treatment)	Baseline	National Patient Registry data used to define CCI in DBCG registry	Not applicable
Number of comorbidities (calculated at start of palbociclib treatment)	Baseline	National Patient Registry data used to define CCI in DBCG registry	Not applicable
Types of comorbidities (Cardiac disease, Vascular disease, Metabolic disease, Psychiatric disease, Blood and lymphatic system) (at start of palbociclib treatment)	Baseline	National Patient Registry data used to define CCI in DBCG registry	Not applicable
Death date	Baseline charac.	DBCG registry	Not applicable
PFS (see section 8.1 for definition)	Outcome	Estimated via DBCG registry	Based on variables listed in this table
OS (see section 8.1 for definition)	Outcome	Estimated via DBCG registry registrations	Based on variables listed in this table

4.4. Data sources

This study will be based on the DBCG clinical database and the National Patient Registry (LPR) with respect to the comorbidities. Data from the DBCG clinical database and the National Patient Registry will be combined by the personal identification codes (CPR) that every Danish citizen has.

4.5. Sample size and power calculations

The study is purely descriptive and explorative. No formal hypotheses will be tested in the study. Calculation of sample size is therefore not applicable.

The expected and estimated total study population with the focus on all Danish mBC patients (endocrine sensitive, endocrine resistant or de novo) that have received palbociclib in combination with AI as first-line therapy. 580 patients will be included from 1 January 2017 to 31 December 2021.

Subgroup analyses of this patient population will be made based on age and comorbidity.

4.6. Missing Data

The study will only include patients for whom there are complete registrations in the DBCG register. However, should missing data occur, no imputation will be made, and all statistics will be calculated with non-missing values. Counts and percentages of missing values will be presented in the tables where applicable.

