## 9. RESEARCH METHODS

### 9.1. Study Design

The study is designed as a secondary data collection NI-Study. Retrospective data will be collected from an existing registry - the DBCG registry. The focus of this study will be on HR+/HER2- locally advanced or metastatic breast cancer treated with palbociclib. The study is a single-arm study focusing on patients treated with palbociclib in Denmark.

The study is purely descriptive and explorative. No formal hypotheses will be tested in the study.

Since the establishment in 1976, the DBCG has maintained a clinical registry for early breast cancer patients in Denmark in which surgeons, pathologists, medical geneticists and oncologists report data regarding diagnosis, treatment and follow-up of breast cancer (39,40). This is a unique clinical registry. This well-established breast cancer registry (1976) managed by DBCG was expanded in 2017 to include retrospective and prospective clinical and pathological data on breast cancer patients with a relapse. This includes both the primary mBC (De Novo) and recurrent mBC.

The DBCG registry focusing on relapses on which the study will be based is one of several DBCG registries. All Danish patients with locally advanced or metastatic breast cancer are included in the DBCG registry. The data and records in the registry are based on systematic review following a standard case report form of all electronic patient records of patients diagnosed with locally advanced or metastatic breast cancer.

PFIZER CONFIDENTIAL

The data collection and the ongoing populating of the DBCG registry are performed by healthcare professionals in the DBCG secretariat and are conducted independently of this study. Compared to other exhaustive national Danish patient registries, the DBCG registry contains detailed clinical and pathological data about the treatment patterns of patients with HR+/HER2- locally advanced or metastatic breast cancer. Thus, the registry is an important and well-suited source to address the research questions of the present study and has previously been used to analyze treatment outcomes for all first- and second-line palbociclib patients in Denmark (29).

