The present NI-Study will therefore rely on data in the DBCG registry, as well as data from the National Patient Registry (comorbidity data). No additional data will be collected as part of the study, furthermore no review of medical records will be made. Therefore, the present NI-Study is defined as a retrospective secondary data collection study, where all data needed for the analysis exist as structured data by the time of study start. This also means that there is no human review of unstructured data conducted as part of the protocol.

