## 9.7. Data Management

The Danish Breast Cancer Group hosts the DBCG registry, and all analyses will be performed by DBCG's biostatistical researchers following this protocol and a pre-specified SAP. Pfizer will not have access to data at the individual level – only summary data in tables produced by DBCG as part of the discussion of results and reporting.

The individual-level patient data in the registry are well-structured, of high quality, and in a ready-to-analyze format. Data will be analyzed using SAS software.

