4.2. Study population

In the DBCG registry, all HR+/HER2- locally advanced or mBC patients treated with palbociclib in combination with AI as first-line treatment will be identified. Palbociclib was approved by the European Commission (EC) and European Medicines Agency (EMA) in November 2016. Hence, the study period will be from 1 January 2017 and to 31 December 2021. A follow-up on patients until 31 December 2023 in terms of the estimation of PFS and OS will be made. The study will only include patients treated with palbociclib+AI as first-line treatment.

Inclusion Criteria

Patients must meet the following inclusion criteria to be eligible for inclusion in the study:

1. *Patients with breast cancer (ICD-10: DC50)*
2. *A diagnosis of HR+/HER2- locally advanced or metastatic breast cancer*
3. *Endocrine sensitive, endocrine resistant, or de novo mBC patient*
4. *Initiated treatment with palbociclib as first-line treatment (palbociclib + AI) between 1 January 2017 and 31 December 2021*
5. *Inclusion data: Data of relapse/stage IV disease/progression leading to initiation of palbociclib+AI*

Exclusion Criteria

There are no exclusion criteria for this study.

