4.7.2. Primary analyses

As primary analyses (descriptive) of PFS and OS will be estimated for all Danish mBC patients receiving palbociclib as first-line treatment in combination with AI. PFS will be estimated for all patients until either a physician-assessed disease progression occurred, death or until data cut-off by 31 December 2023. OS will be estimated for all patients with a censoring of data by 31 December 2023 as the last day of data capture in the study.

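### SAP 4.6 restricts the study to patients with undefined complete registrations; as written this contradicts the stated absence of exclusion criteria, and no planned output counts anyone left out

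*SAP*

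**What the plan says.** The sentence at issue is in the missing-data section, SAP 4.6: "The study will only include patients for whom there are complete registrations in the DBCG register". It continues: "However, should missing data occur, no imputation will be made, and all statistics will be calculated with non-missing values". The section then plans counts and percentages of missing values in the tables. It does not say which fields make a registration complete.

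The population is defined elsewhere. SAP 4.2 and Protocol 9.2.1 list the same five inclusion criteria, none of which concerns record completeness. Both documents then state: "There are no exclusion criteria for this study". SAP 4.7.2 says of the primary analyses that "PFS and OS will be estimated for all Danish mBC patients receiving palbociclib as first-line treatment in combination with AI".

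The table shells in SAP Appendix A start from patients already included, who form the 100% row of Table 1. No text or shell gives the number identified in the registry, the number eligible or the number left out.

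**The concern.** An analyst who applies SAP 4.6 as written and one who applies SAP 4.2 and 4.7.2 could analyse different cohorts for both primary objectives. The first would select patients on the state of their registry record, by a rule each analyst has to invent.

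If incompleteness is unrelated to outcome, the only loss is sample size. If it is related to outcome, the medians are biased, in a direction that cannot be known in advance. Protocol 9.10 rests the study's generalisability on population-level coverage and on a low risk of selection bias. Without a count of patients left out, a reader cannot check that claim.

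**Working it through.** **Text comparison**

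| Place | Who is analysed |
|---|---|
| SAP 4.2, Protocol 9.2.1 | Patients meeting five criteria, none on completeness |
| SAP 4.2, Protocol 9.2.2 | No exclusion criteria |
| SAP 4.7.2 | All eligible Danish patients |
| SAP 4.6, first sentence | Only those with complete registrations |
| SAP 4.6, second sentence | Missing values tolerated, available data used |
| SAP Appendix A | Starts at included patients; nobody left out is counted |

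The first sentence of SAP 4.6 either removes eligible patients, and so conflicts with the first three rows, or removes nobody and has no function. The planned counts of missing values do not settle which, because they cover included patients only.

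**Size, as an illustration only**

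The plan has no figure to reproduce. The 580 is an estimated registry count (Protocol 9.6, SAP 4.5), and no completeness rate is given.

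Inputs from the documents:
- N = 580.
- Medians of 31.3 months (PFS) and 56.9 months (OS), from the earlier Danish registry study in Protocol 7. Those are for endocrine-sensitive patients; this cohort also includes endocrine-resistant patients.
- Entry from January 2017 to December 2021 (60 months) and cut-off 1 February 2024 (month 85).

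Assumptions: exponential event times, uniform entry, and a loss of 12, 29 or 58 patients (about 2%, 5% and 10%).

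1. *Share with an event by cut-off.* Follow-up runs from 25 to 85 months, so p = 1 − [exp(−25λ) − exp(−85λ)]/(60λ), with λ = ln 2/median.
   - PFS: λ = 0.02215, p = 1 − (0.575 − 0.152)/1.329 = 68.2%.
   - OS: λ = 0.01218, p = 1 − (0.738 − 0.355)/0.731 = 47.7%.
2. *Removal risks under a 2:1 imbalance, total loss q.* If event-free patients are twice as likely to be lost, patients with events have risk r = q/[p + 2(1 − p)] and event-free patients 2r. At q = 10% for PFS, r = 0.10/1.318 = 7.6%, against 15.2%. For OS the risks are 6.6% and 13.1%. In the reverse case, event-free patients have risk s = q/[2p + (1 − p)] and patients with events 2s: 5.9% and 11.9% for PFS, 6.8% and 13.5% for OS.
3. *Kaplan-Meier median among those kept.* The hazard at t is the retained event density divided by the retained proportion at risk, integrated numerically until survival reaches 50%.

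| Removal pattern | PFS median (loss 12 / 29 / 58) | OS median (loss 12 / 29 / 58) |
|---|---|---|
| At random | 31.3 / 31.3 / 31.3 | 56.9 / 56.9 / 56.9 |
| Event-free 2:1 | 31.1 / 30.7 / 30.1 | 56.4 / 55.5 / 54.1 |
| Events 2:1 | 31.5 / 31.8 / 32.3 | 57.5 / 58.4 / 60.1 |
| All 58 event-free | 27.0 | 49.4 |
| All 58 with events | 33.8 | 67.9 |

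4. *Comparison with sampling error.* The simulated 95% range of the median at n = 580 is 27.6 to 35.2 (PFS) and 49.9 to 65.2 (OS). Every 2:1 value lies inside. The largest shifts are 31.3 − 30.1 = 1.2 months and 60.1 − 56.9 = 3.2 months. In the extreme one-class case three of the four medians leave the range: PFS 27.0, OS 49.4 and OS 67.9. The first two do so by only 0.6 and 0.5 month. PFS 33.8 stays inside.

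Using the SAP's cut-off of 31 December 2023 (month 84) leaves the 2:1 values essentially unchanged.

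**The case against.** The best defence is that the sentence states an expectation about data quality and is not a filter. It sits under missing data, not eligibility, and the sentence after it makes sense only if records with gaps stay in. The protocol supports this view of the registry: "The data and records in the registry are based on systematic review following a standard case report form of all electronic patient records"; "all data needed for the analysis exist as structured data by the time of study start"; "The individual-level patient data in the registry are well-structured, of high quality, and in a ready-to-analyze format". The study is also descriptive, with no hypothesis tests. Much of this stands. It makes the no-exclusion reading plausible and limits the severity. It does not remove the conflict, because the restriction is still written and undefined, and neither document gives a completeness rate. If the softer reading is intended, deleting the sentence costs nothing.

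Two stronger readings are tempting and are not supported:

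- *Completeness requires every listed variable.* The list in SAP 4.3 includes "Date for treatment stop with palbociclib" and the death date, which are blank for patients still on treatment or alive. A reader might infer that the rule selects directly on outcome. SAP 4.7.2 plans censoring of OS and follow-up for PFS to a data cut-off, which presupposes patients without an event. That reading is therefore ruled out, and only ordinary field completeness remains unclear.
- *The primary medians are materially biased.* The documents support no loss rate and no imbalance, and the moderate scenarios stay within sampling error.

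A further objection concerns the remedy. If everyone is included and all patients without a recorded event are treated as event-free to cut-off, unrecorded follow-up becomes survival. Under the same model, with an assumed 2%, 5% or 10% of patients having unrecorded outcomes, the medians become 32.2, 33.7 and 36.6 (PFS) and 58.6, 61.3 and 66.6 (OS). At 10% that is 36.6 − 31.3 = 5.3 and 66.6 − 56.9 = 9.7 months too long, more than any 2:1 exclusion scenario. This objection stands, and the fix allows for it.

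**Conclusion.** The concern holds as a contradiction in the text combined with a missing count. SAP 4.6 contains an undefined inclusion restriction that conflicts with the eligibility sections of both documents and with the all-patient primary analyses, and nothing planned would show its effect. No actual exclusion or bias is demonstrated: the number affected is unknown and may be nil. The illustrated shifts of about 1 month (PFS) and 3 months (OS) rest on an assumed 10% loss, an assumed 2:1 imbalance, exponential times and medians from a related but narrower group. Severity is minor to moderate.

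**What to change.** 1. Reconcile the censoring dates first, because the rest depends on them. Protocol 8.1 gives 1 February 2024 for PFS and OS. SAP 4.7.1 gives 31 December 2021 for PFS. SAP 4.7.2 gives 31 December 2023 for both.
2. Delete the first sentence of SAP 4.6 and include every patient who meets inclusion criteria 1 to 5. Keep the rule of no imputation with counts of missing values.
3. Leave a patient out of a PFS or OS estimate only if the index date is missing, and report how many.
4. Carry a patient to the data cut-off only where the registry confirms that the patient is event-free to that date. Where progression or vital status is not recorded to cut-off, censor at the last date with recorded status and report the number.
5. Add a flow count to Appendix A: identified in the registry, eligible, not analysed (with reason), analysed.

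The cost is one deleted sentence, a short censoring rule and one small table. Some subgroup tables will carry a small missing category, and some patients will be censored earlier than the cut-off.

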4.7. Statistical methodology and analyses

The study is a single-arm study and will be purely descriptive and explorative. No formal hypotheses will be tested.

This study will provide two types of outcomes:

1. Outcomes on PFS and OS of patients treated with palbociclib+AI as first-line (population and subpopulations (Age and Comorbidity) (Appendix A, Table 3 and 4))
2. Descriptive statistics on the population/subpopulations treated with palbociclib+AI (Appendix A, Table 1 and 2)

4.7.1. Index date and follow-up

Definitions of the incidence data and the index date of the first-line treated palbociclib + AI patients shown together with the definition of the treatment outcomes (PFS and OS), as well as definition of visceral disease can be found in the table below.

Incidence date	The date of the initial breast cancer diagnosis.
Index date	The date of relapse or stage IV disease.
Progression Free Survival (PFS)	The time from the date of relapse or stage IV disease (index date) to progression or death, whichever occurs first. Patients will be censored 31 December 2021. Progression is based on radiological, clinical, and biochemical examination from the treating departments.
Overall Survival (OS)	The time from index date to death at any cause.
Visceral disease	Defined as metastases in the organs, e.g., lung, liver. Visceral disease is based on the variable Location of metastases (RE10-18 + 80-81, 117-119, 219-222) in the DBCG database.

For the PFS and OS outcomes for the full palbociclib first-line population (primary analyses) as well as each subpopulation (secondary analyses), as presented below, Kaplan-Meier survival distribution functions with 95% confidence intervals will be estimated. Hence, if possible median PFS and OS as well as interquartile ranges (IQR) will be estimated. Unadjusted Kaplan Meier curves will be presented to illustrate time-to-event (PFS or OS).

For the descriptive statistics, numbers and percentages will be provided and presented in tables, including cross tabulations (see section 6 for presentation of tables shells).

All data analysis will be executed using the statistical software R-studio.

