## 8. RESEARCH QUESTION AND OBJECTIVES

The overall objective is to retrospectively investigate the outcomes (overall PFS and OS) of first-line treatment with palbociclib in combination with an AI in key subgroups of mBC patients in Denmark focusing on age and comorbidity burden.

Primary objectives:

- PFS of all mBC patients receiving palbociclib in combination with AI as first-line treatment
- OS of all mBC patients receiving palbociclib in combination with AI as first-line treatment

Secondary objectives:

- *Age subgroup analyses:*
  - Age distribution in the full data set of mBC patients receiving palbociclib + AI as first-line treatment
  - PFS and OS in mBC patients below 65 years of age, 65-74 years of age and 75+ years of age, respectively, receiving palbociclib + AI as first-line treatment
- *Comorbidity subgroup analyses* (Charlson Comorbidity Index (CCI) (38) is used as a data source for comorbidity and comorbidity burden – comorbidities at start of palbociclib treatment):
  - PFS and OS in the full dataset of mBC patients receiving palbociclib + AI as first-line treatment split into CCI point scores of 0, 1, 2, and 3 or higher (3+)

- PFS and OS in the full dataset of mBC patients receiving palbociclib + AI as first-line treatment split into number of comorbidities (no comorbidity, one comorbidity, and two or more comorbidities)
- PFS and OS in the full dataset of mBC patients receiving palbociclib + AI as first-line treatment split into type of comorbidity – focus on five main groups: Cardiac disease, Vascular disease, Metabolic disease, Psychiatric disease, Blood and lymphatic system.

Following the inclusion criteria (see section 9.2.1 below) the analyses will be performed on the full data set of patients with HR+/HER2- locally advanced or metastatic breast cancer treated with palbociclib + AI as first-line treatment.

As stated, the research questions will be addressed and analysed using the DBCG registry (see section 9.1 for a description of the registry).

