### 8.1. Definitions

PFS is defined as the date of relapse or stage IV disease (index date) to progression or death, whichever occurs first.

- Patients will be censored for PFS by 1st February 2024
- Progression of disease is based on scans and blood testing results

OS is defined as the date of relapse or stage IV disease (index date) until death of any cause.

- Patients will be censored for OS by 1st February 2024

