### **9.2.1. Inclusion Criteria**

Patients must meet the following inclusion criteria to be eligible for inclusion in the study:

1. Patients with breast cancer (ICD-10: C50)
2. A diagnosis of HR+/HER2- locally advanced or metastatic breast cancer
3. Endocrine sensitive, endocrine resistant, or de novo mBC patient
4. Initiated treatment with palbociclib as first-line treatment (palbociclib + AI) between 1 January 2017 and 31 December 2021
5. Inclusion date: Date of relapse/stage IV disease/progression leading to initiation of palbociclib + AI

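### OS and PFS run from relapse or stage IV in a cohort defined by later starting palbociclib + AI; read as treatment outcomes, median OS includes the unreported gap before first dose

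*SAP*

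**What the plan says.** Both documents place time zero at relapse or stage IV disease. SAP section 4.7.1 defines PFS as "The time from the date of relapse or stage IV disease (index date) to progression or death, whichever occurs first" and times OS from the same index date. Protocol section 8.1 matches: "OS is defined as the date of relapse or stage IV disease (index date) until death of any cause".

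Entry to the cohort depends on a later event. Protocol section 9.2.1, item 4, requires: "Initiated treatment with palbociclib as first-line treatment (palbociclib + AI) between 1 January 2017 and 31 December 2021". Item 5 sets the inclusion date as "Date of relapse/stage IV disease/progression leading to initiation of palbociclib + AI". SAP section 4.2 adds: "The study will only include patients treated with palbociclib+AI as first-line treatment".

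The estimator is Kaplan-Meier with 95% confidence intervals, and "Unadjusted Kaplan Meier curves will be presented to illustrate time-to-event (PFS or OS"). No delayed entry, landmark or from-first-dose analysis is planned.

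On interpretation, Protocol section 8 sets out to "investigate the outcomes (overall PFS and OS) of first-line treatment with palbociclib in combination with an AI", SAP section 3 has the same aim, and SAP section 4.7.1 introduces its table as giving the "definition of the treatment outcomes (PFS and OS"). The date of palbociclib initiation (RE203-RE205) is a listed variable in both documents, but no shell in SAP Appendix A reports the interval from index date to that date.

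**The concern.** Anyone who died between relapse and a planned first dose is absent from the data by design. For every included patient that interval is therefore survival time guaranteed by the selection rule, and an ordinary Kaplan-Meier from relapse counts it in full. As a description of survival since relapse among patients who later started treatment, this is coherent. As an outcome of palbociclib + AI, it credits the treatment with time before it was given.

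The medians and curves are the main product of this study, so what they measure matters. A reader cannot judge how much of the median is pre-treatment time, because the planned output shows neither the gap nor the result from first dose. The limitations in Protocol section 9.10 do not mention the point.

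**Working it through.** **1. The plan's own follow-up figure.** Protocol section 9.8 gives a maximum follow-up of 7 years and one month. From 1 January 2017 to 1 February 2024 is 2,587 days, and 2,587 / 30.4375 = 85.0 months, so the figure reproduces. It counts from treatment. On the relapse clock, a patient who relapsed in 2016 and started in January 2017 would have longer follow-up. This is a point of wording, not a second endpoint definition.

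**2. Inputs.**
- Medians for scale only: OS 56.9 and PFS 31.3 months (Protocol section 7, earlier Danish registry study, first-line endocrine-sensitive AI group). The protocol does not state their time origin; here they stand in for medians from first dose.
- N = 580 (Protocol section 9.6, SAP section 4.5).
- Mean gap g from index date to first dose: not in the documents. Assumed 1 to 3 months, with 0.5 and 6 as outer values.

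**3. Shift in the median if no pre-dose event is counted.** With a fixed gap, median from index = m + g. With exponential survival from first dose (rate λ = ln 2 / m) and an exponential gap of mean g,

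S(t) = [exp(−λt) − λg·exp(−t/g)] / (1 − λg),

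whose median is close to m − ln(1 − λg)/λ. For OS with g = 1: λ = 0.6931/56.9 = 0.01218, and −ln(1 − 0.01218)/0.01218 = 1.006, giving 57.91. Exact results in months:

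| Mean gap | OS, fixed | OS, exponential | PFS, fixed | PFS, exponential |
|---|---|---|---|---|
| 0.5 | 57.4 | 57.40 | 31.8 | 31.80 |
| 1 | 57.9 | 57.91 | 32.3 | 32.31 |
| 2 | 58.9 | 58.92 | 33.3 | 33.35 |
| 3 | 59.9 | 59.96 | 34.3 | 34.40 |
| 6 | 62.9 | 63.13 | 37.3 | 37.71 |

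**4. Against sampling error.** Simulation with N = 580, starts uniform over 60 months, cut-off at month 85 and 2,000 runs gives a standard error of the from-first-dose median of about 4.0 months (OS) and 1.9 months (PFS). A 1-month gap is then 1/4.0 = 0.25 SE for OS and 1/1.9 = 0.5 SE for PFS; a 3-month gap is 0.75 SE and 1.6 SE. Running both origins in the same patients shows the shift far more precisely: at a 1-month mean gap the paired difference in medians is 1.02 months for OS (95% range 0.07 to 2.45) and 1.00 for PFS (0.38 to 1.78).

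**5. PFS if pre-dose progression counts as an event.** If a share p progresses before first dose, the later curve is multiplied by (1 − p). This cancels the gap effect at about p = λg. With λ = 0.6931/31.3 = 0.02214, that is 2.2%, 4.4% and 6.6% for mean gaps of 1, 2 and 3 months. Above that share, PFS shifts downward. These shares are hypothetical and show only that the direction is open.

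**6. Subgroups.** Each subgroup median shifts by about that group's own mean gap. Assumed gaps of 1 and 3 months in two groups would create a difference of 3 − 1 = 2 months. Equal gaps would create about none.

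**7. Delayed entry as a remedy.** Median OS in months, mean gap 3 months:

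| Gap distribution | Ordinary, from index | Delayed entry | From first dose |
|---|---|---|---|
| Exponential | 60.2 | 57.1 | 57.2 |
| Uniform 1 to 5 | 59.94 | 58.05 | 56.93 |
| Uniform 2 to 4 | 59.70 | 58.78 | 56.71 |
| Fixed 3 | 59.99 | 59.99 | 56.99 |

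Delayed entry leaves a shift of about the shortest gap: essentially none when some gaps are near zero, and all of it when the gap is identical for everyone.

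**The case against.** The strongest reply is that this is a choice of estimand, stated openly. The definition agrees across both documents, the notes to SAP Tables 3 and 4 refer back to it, and the primary objectives speak of PFS and OS of patients receiving palbociclib + AI, which fits a relapse origin. Inclusion ties the index event to the one that led to first-line palbociclib, so long gaps may be uncommon. At a 1-month gap the shift is well inside the planned confidence intervals.

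Most of this stands. Relapse or stage IV is a legitimate origin and there is no case for replacing it as primary. What does not follow is that the gap can go unreported. No maximum interval is set, the objectives also use treatment-outcome language, and sampling error does not excuse a systematic shift that existing data can measure directly.

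Some stronger readings are tempting, and the documents do not support them:
- A reader might infer that the primary OS is simply biased. That holds only against survival from first dose, which the plan never names as its target.
- A reader might infer that guaranteed survival time exaggerates a benefit of palbociclib over an alternative. The study has a single arm and no comparator.
- A reader might infer that PFS is lengthened just as OS is. SAP section 4.7.1 does not say how progression before first dose is handled. The mention of progression in inclusion item 5 could move the inclusion date to such an event, but no rule says so.

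**Conclusion.** The point holds as a matter of interpretation and reporting. When OS is read as an outcome of palbociclib + AI, its median is longer by about the mean relapse-to-start gap, and that direction is certain. For PFS the direction depends on an unstated rule.

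The size is unknown. Under assumed mean gaps of 1 to 3 months it is about 1 to 3 months for OS, and for PFS if no pre-dose progression is counted, against sampling standard errors of about 4 and 1.9 months. This rests on exponential survival, 580 patients, and medians borrowed for scale.

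On subgroups, two opposite inferences both go too far. One is that the age and comorbidity contrasts are distorted: that requires the gap to differ between groups, and the documents are silent on this. The other is that a descriptive study has no test to affect: SAP section 4.7.3 plans tests of PFS and OS differences across subgroups, and these are affected to the extent that gaps differ.

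**What to change.** - Keep the relapse-origin analysis as primary.
- Add a companion Kaplan-Meier analysis of PFS and OS from palbociclib initiation (RE203-RE205), overall and by subgroup, marked with the date it was added. Delayed entry at first dose is an acceptable alternative when some gaps are near zero, with the limit shown in step 7.
- Add the relapse-to-start gap (median, IQR, maximum) to SAP Table 1, overall and by age and CCI group.
- Label SAP Tables 3 and 4 and the curves as survival since relapse or stage IV among patients who started palbociclib + AI.
- As a clarification, state in SAP section 4.7.1 how progression between index date and first dose is treated.

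The cost is one extra set of medians and curves, a few table rows and some sentences, with no new data. The companion medians will be slightly shorter if gaps are short. Changing the primary origin instead would cost more, because Protocol section 9.8 requires an amendment for major changes to primary endpoint definitions. Analyses were scheduled for 22 April to July 2024 and protocol version 3.0 is dated 17 February 2025, so the addition may post-date the scheduled analysis; dating it makes that visible.
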